3.10.2.2 Main Analysis

Blood pressure values will be summarized using descriptive statistics, including actual values and changes from Baseline (week prior to Randomization) to Week 4, by timepoint and treatment groups. Graphical presentations of group means over time will be presented on the Randomized Set by treatment group. Additional summaries may be presented.

The difference in change from Baseline to Week 4 will be analyzed using MMRM. The endpoint will be the FU1/Week 4 home SBP values with fixed effects for treatment group and Baseline home SBP. The variance will be estimated using a Huber-White sandwich estimator, with the model accounting for correlation within site. A compound symmetry covariance matrix will account for correlation within site with a fall back of an independent matrix if the model does not converge.

Least Square Means and corresponding standard errors will be estimated for each post-Baseline visit and treatment group. Pairwise comparisons between GMRx2 and placebo will be performed at Week 4. The comparisons at Week 4 will serve as the primary endpoint analysis. As an exploratory assessment, a comparison between GMRx2 dose levels will also be presented.

Sample SAS Code:

```
PROC MIXED DATA = ADEFF EMPIRICAL METHOD = REML;
  CLASS SITEID SUBJID VISIT TRTP;
  MODEL AVAL = BASE TRTP / CL;
  REPEATED / SUBJECT = SITEID TYPE = CS;
  WHERE VISIT IN ('WEEK4');
  LSMEANS TRTP / DIFF CL ALPHA=0.05;
  RUN;
```

Where ADEFF is the ADaM dataset for efficacy, AVAL represents the Week 4 home SBP measurement, BASE is the Baseline SBP value and TRTP is the planned treatment.

Superiority of the triple combination over the placebo will be shown if the 2 comparisons listed above are statistically significant (when the null hypothesis of equal adjusted means is rejected).

The main analysis of the primary endpoint will be performed using multiple imputation to account for missing data ([Section 3.10.1.1](#); [Section 3.10.2.6](#)).

Supportive analyses will be performed on:

- 1) The Full Analysis Set (if the analysis set differs from the Randomized set by at least 5%) using the same multiple imputation rules as the primary analysis
- 2) Complete Cases with Clinic BP Substitution
- 3) Per Protocol Set excluding participants with intercurrent events or major protocol deviations

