At randomization visit

1. Contraindication to any of the randomized medications including placebo

At week 4 (for optional Open-Label Extension Period)

1. Contraindication to any of the open-label GMRx2-based BP-lowering treatment regimen.

TRIAL MEDICATIONS:

A 2-week single-blind placebo run-in followed by a 4-week double-blind period with randomization to one of the following three trial medication groups:

Group	Intervention	N	Treatment
1	GRMx2 Dose version 1: Triple ¼	100	telmisartan 10 mg/amlodipine 1.25 mg/indapamide 0.625 mg
2	GRMx2 Dose version 2: Triple ½	100	telmisartan 20 mg/amlodipine 2.5 mg/indapamide 1.25 mg
3	Placebo	50	placebo

An optional 12-month Open-Label Extension Period will commence at Week 4

TRIAL OUTCOMES:**Efficacy Outcomes****Primary**

- Difference in change in home SBP from baseline to Week 4

Key secondary efficacy outcomes

- Difference in change in home DBP and clinic BP from baseline to Week 4.
- Percentage of participants with hypertension control with home and clinic BP at Week 4.

Key Safety Outcomes

- Adverse events (AEs)/serious AEs leading to discontinuation of trial medication from baseline to Week 4.
- Serious AEs from baseline to Week 4

In addition, descriptive, non-comparative data on mean BP, BP control, and safety outcomes will be reported on the cohort of participants entering the optional Open-Label Extension Period.

NUMBER OF PARTICIPANTS & TRIAL POWER:

A total of 250 participants will be randomized, which may necessitate over 300 entering the placebo run-in treatment period. For the comparison of triple ¼ vs placebo at Week 4, a sample size of 150 participants at a ratio of 2:1 will provide 90% power to detect a difference of at least 9 mmHg in mean home SBP, assuming a standard deviation of 11 mmHg.

NUMBER OF COUNTRIES & TARGET NUMBERS OF SITES:

Approximately 25-30 sites in Australia, Sri Lanka, Nigeria, UK and USA.

TRIAL PERIOD:

Placebo run-in treatment period: 2 weeks

Randomization treatment period: 4 weeks

Safety follow-up period: 4 weeks

Optional Open-Label Extension Period: 12 months (selected countries only)

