2 INTRODUCTION

2.1 Trial Objective

This trial is an international, multi-center, parallel-group, double-blind, randomized, placebo-controlled trial to investigate the efficacy and safety of GMRx2 compared to placebo for the treatment of hypertension.

Section 5 of the Protocol introduces the history and development of combination therapies for treatment of hypertension and describes the potential role of triple low-dose combination and expected effects.

This statistical analysis plan (SAP) defines derivations, algorithms, key components and statistical analysis methods to be applied in the analysis and summary of data collected in the study GMRx2-HTN-2020-PCT1. Sample SAS programming code is provided for a select group of statistical models. This code is provided as example and may require modifications to accommodate the data collected.

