2.3.2 Randomization

Randomization (permuted with variable block sizes and stratified by trial site) will be conducted via a password-protected, secure website/interactive voice response service. Following successful randomization, each participant will be assigned a unique 'participant study number' and be allocated to receive either placebo or one of the GMRx2 doses. The ratio of randomization will be 2:2:1, as shown below:

1. **Triple ¼ (GMRx2 dose 1):** N=100
2. **Triple ½ (GMRx2 dose 2):** N=100
3. **Placebo:** N=50

Study participants, treating clinicians, study investigators and data collectors will be blinded to treatment group assignment.

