2.6 Changes in the Conduct of the Study or Planned Analyses

2.6.1 Changes in the Conduct of the Study

A total sample size of 250 participants was planned; however due to a number of high recruiting centres starting at a similar time towards the end of the study a total of 295 participants were randomized.

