3.3 Multiplicity Adjustment

All tests are to be two-sided with a nominal level of α set at 5%. Since the purpose of the trial is to demonstrate effects on both of the GMRx2 dose versions versus placebo comparisons simultaneously for the designated primary endpoint (i.e., each GMRx2 dose has to be statistically significantly superior at two-sided $p<0.05$ to placebo for the trial to be regarded as positive), there is no need for adjustment of the Type I error for the primary endpoint, according to ICH E9 Guidance and FDA Guidance 'Multiple Endpoints in Clinical Trials. Guidance for Industry, 2022'.

The secondary efficacy parameters measure different aspects of the same underlying treatment effect evaluated in the primary efficacy endpoint, that is the effect of GMRx2 compared to placebo on blood pressure and do not demonstrate additional new treatment effects of the drug, but rather clarify the effect already demonstrated by the primary analysis. No type I error adjustment is proposed to adjust secondary efficacy endpoint analyses.

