3.10.2.5 Subgroup and Additional Analyses

Pre-specified subgroup analyses will be carried out irrespective of whether there is a statistically significant treatment effect on the primary endpoint. Subgroups are defined as follows:

- Sex (Male; Female)
- Age (<55; 55-65; > 65 years)
- Race (black; non-black)
- BMI (<30, >=30 kg/m²),
- Diabetic; non-diabetic,
- Region (USA; Other)
- Placebo run-in single-blinded (yes/no)*
- Baseline (at Randomization) home SBP category (<140, 140-149, ≥150 mmHg) and DBP category (<80, 80-89, ≥90 mmHg)
- Number of BP medications at Screening (0, 1)
- Hypertension status at Screening – office BP <140/90 mmHg, ≥140/90 mmHg; office BP <130/80 mmHg, ≥130/80 mmHg
- Orthostatic (postural) hypotension at Randomization (measured at clinic BP): see [Section 3.10.3.2](#) for definitions.

* UK authorities required unblinded run-in period, non-UK centres had single blinded run-in period.

Subgroup analyses will be performed by inclusion of the subgroup main effect as well as two-way interaction terms as fixed effects with treatment within the MM. Heterogeneity of treatment effect between subgroups will be evaluated using contrast statements, to test whether the LS Mean difference between GMRx2 and placebo group differs between levels of the subgroup. Comparisons will be performed separately for each GMRx2 dose level against placebo. A comparison of combined GMRx2 doses against placebo by subgroups will also be performed. LS Means, LS Mean Differences and 95% CIs will be reported for each category of subgroup. If any subgroup does not have sufficient participants for statistical modelling

(i.e., model convergence), descriptive statistics will be provided. A forest plot will also be provided to visualize the overall subgroup analysis.

Sample SAS Code accounting for Sex as Subgroup:

```
PROC MIXED DATA = ADEFF EMPIRICAL METHOD = REML;
  CLASS SITEID SUBJID VISIT TRTP SEX;
  MODEL AVAL = BASE TRTP|SEX / CL;
  REPEATED / SUBJECT = SITEID TYPE = CS;
  WHERE VISIT IN ('WEEK4');
  LSMEANS TRTP*SEX / DIFF CL ALPHA=0.05;
  lsmeans estimate trtp*sex "(TS11-TS31)-(TS12-TS32)"
    [1, 1 1] [-1, 3 1] [-1, 1 2] [1, 3 2]; *TRTP=1 vs TRTP=3;
  lsmeans estimate trtp*sex "(TS21-TS31)-(TS22-TS32)"
    [1, 2 1] [-1, 3 1] [-1, 2 2] [1, 3 2]; *TRTP=2 vs TRTP=3;
  RUN;
```

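### The site-clustered sandwich variance has no small-sample correction or site-based degrees of freedom for about 25-30 sites, so the 5% tests run mildly above 5%, and the UK/non-UK heterogeneity test more so

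*SAP*

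**What the plan says.** The main analysis in SAP 3.10.2.2 regresses Week 4 home SBP on baseline and treatment, with compound symmetry within site and an independence structure as fall-back. On the standard error it says: "The variance will be estimated using a Huber-White sandwich estimator, with the model accounting for correlation within site". The sample code uses EMPIRICAL without a small-sample option and no DDFM option. The pooling step in 3.10.2.6 calls PROC MIANALYZE without EDF. SAP 2.1 says of the code: "This code is provided as example and may require modifications to accommodate the data collected". The sandwich itself is in the prose and does not depend on the code.

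The number of clusters comes from the protocol synopsis: "Approximately 25-30 sites in Australia, Sri Lanka, Nigeria, UK and USA". SAP 2.6.1 reports that "a total of 295 participants were randomized" and attributes the overshoot to high-recruiting centres. SAP 2.3.2 describes the allocation as "Randomization (permuted with variable block sizes and stratified by trial site", in a 2:2:1 ratio.

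Under SAP 3.3 there is no alpha adjustment, because "each GMRx2 dose has to be statistically significantly superior at two-sided" p<0.05. SAP 3.10.2.5 applies the same model to subgroup interactions, "to test whether the LS Mean difference between GMRx2 and placebo group differs between levels of the subgroup". One subgroup is blinding of the run-in, with the footnote "UK authorities required unblinded run-in period, non-UK centres had single blinded run-in period".

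**The concern.** A site-clustered sandwich estimates variance from one residual contribution per site. With 25-30 contributions, fewer in effect if sites are unequal, it is too small on average and itself variable. Referring the statistic to a t distribution with several hundred df ignores that variability.

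SAP 3.3 leaves error control entirely to each pairwise test being a true 5% test. If the standard error is too small, the tests exceed 5% and the 95% intervals are too narrow. The tipping-point analysis in 3.10.2.7, which stops when p exceeds 0.05, would also look more robust than it is. No listed analysis would reveal this. The supportive sets, pooled-dose, adjusted and subgroup analyses change the population, contrast or covariates, but never the variance estimator.

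The run-in-blinding subgroup is more exposed. Every participant at a site has the same level, so the treatment interaction rests on the UK sites alone on one side. A false signal there would be read as evidence that an unblinded run-in altered the drug effect.

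**Working it through.** **Inputs from the documents.** Two-sided 5% per comparison and the both-doses rule (SAP 3.3); 25-30 sites (protocol synopsis); 295 randomized (SAP 2.6.1); 2:2:1 in permuted blocks within site (SAP 2.3.2); SD 11 mmHg and effect 9 mmHg (protocol 12.3, SAP 2.5).

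**Inputs assumed, because the documents do not give them.** Site-size spread, site intraclass correlation (ICC), number of UK sites, block sizes of 5 or 10.

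**Step 1: the plan's own figure.** For 100 against 50, SE = 11 × √(1/100 + 1/50) = 1.905. Power = Φ(9/1.905 − 1.960) = Φ(2.764) = 99.7%, as SAP 2.5 states. For 100 against 100, SE = 11 × √(2/100) = 1.556 and Φ(4.5/1.556 − 1.960) = 82.5%, matching the >80% in protocol 12.3.

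**Step 2: SE at 295.** The 2:2:1 split is 118:118:59, so SE = 11 × √(1/118 + 1/59) = 1.75 before allowing for site correlation.

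**Step 3: size of the test as written.** Two separately programmed simulations, each with 4,000 null trials per main scenario and two dose contrasts per trial (Monte Carlo error about 0.3 points). Both fit the SAP model by REML with compound symmetry. The uncorrected sandwich is referred to t on within-site df, 295 − sites − 3 = 262 to 267 in simulation B. This is taken to be the PROC MIXED default when DDFM is omitted. Data were complete; imputation was not modelled. ICC was 0.02-0.10 in A and 0.03 in the main B scenarios. The corrected version is the Mancl-DeRouen sandwich, with t on sites − 1 df in A and sites − 2 in B.

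| Each dose vs placebo, 25-30 sites | A | B |
|---|---|---|
| As written, equal sites | 6.2-6.7% | 5.9-6.6% |
| As written, moderately unequal (CV 0.8 in A) | 7.0-8.5% | 7.0-7.9% |
| As written, skewed (CV 1.2 in A) | 8.1-8.8% | 8.2-8.4% |
| Corrected, all of the above | 4.4-5.6% | 4.3-5.8% |

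In A the mean sandwich SE was 1.55-1.70 against an empirical SD of 1.66-1.76. In B, site-based df without the bias correction left 5.0-7.5%, so both parts are needed. ICC made no difference in B (7.4% at 0 and at 0.10).

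**Step 4: departures from the model.** Simulation A, 27 sites, CV 0.8, ICC 0.05, with placebo/active SD 13/10 or 10/13, treatment-by-site SD 3 mmHg, or both: 7.3-8.1% as written, 4.9-5.6% corrected, 2.5-10.4% for model-based REML. Model-based standard errors are therefore not a safe replacement.

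**Step 5: the both-doses rule.** The two contrasts share placebo, so their correlation is (1/59)/(1/59 + 1/118) = 2/3. With exact 5% tests and neither dose effective, both would favour GMRx2 in about 0.75% of trials (bivariate normal). As written, A gives 0.9-1.5% in favour and 1.8-3.0% in either direction; B gives 1.5-2.8% in either direction. Under the departures the highest was 2.1% in favour. If one dose clearly works and the other is null, the rule's error approaches the single-comparison rate in Step 3.

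**Step 6: UK/non-UK heterogeneity test.** 27 sites in A; 27 in B except 25-30 for the 3-site row. Monte Carlo error is about 0.4-0.8 points.

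| UK sites (assumed) | As written, A | As written, B | Corrected, A | Corrected, B |
|---|---|---|---|---|
| 13 | 7.5-9.0% | – | 4.3-4.7% | – |
| 8 | – | 10% | – | 5.3% |
| 6 | 10.6-12.7% | 12% | 5.6-5.7% | 5.6% |
| 3 | 19-26% | 19-28% | 9.3-9.5% | 9-10% |
| 2 | – | 36% | – | 12% |

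**Step 7: price of the correction.** In A the CI half-width goes from 3.1-3.3 to 3.5-3.7 mmHg, that is 0.25-0.53 wider. With corrected SE 1.69-1.80 and 26 df, noncentral-t power for 9 mmHg is at least 99.8%. At the worst SE simulated (2.06) it is 98.8%.

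**The case against.** The strongest reply is that this hardly touches the decision. Success needs both doses; if neither works, false success in favour of GMRx2 stays below the 2.5% that one two-sided 5% test allows. The inflation reaches the decision only if one strength of the same combination works and the other does nothing. The protocol plans on 9 and 13 mmHg, so that is unlikely, and only about half of the 6-9% lies in the favourable direction. All of this stands, and it is why the point is a recommended correction and not a threat to the conclusion.

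Second, the SAP does not rule out a correction: it is silent, and the within-site df are inferred from example code. That is fair as to wording. But the estimator is named in the prose, and following the plan as written gives the uncorrected version.

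Third, the sizes rest on assumed site counts and sizes, with complete data. That also stands: the direction is secure, and the figures are illustrative. Equal sites give the low end, but the high-recruiting centres in SAP 2.6.1 make equal sites the less plausible case.

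Fourth, the UK test is one of many uncontrolled heterogeneity tests, and the correction does not restore 5% with 3 UK sites. Both are true. SAP 3.10.2.5 falls back to description only when a model cannot be fitted, which does not cover a model that converges on very few UK sites. Region (USA; Other) is also constant within site and has the same weakness.

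**Conclusion.** The concern holds. As written, each 5% test against placebo runs at about 6-9%, depending mainly on how unequal the sites are, and the 95% intervals are about 0.25-0.5 mmHg too narrow on each side. The UK/non-UK heterogeneity test is inflated more: from roughly 8-9% when UK sites are about half the total to 19-28% with 3.

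These sizes assume 25-30 sites, SD 11 mmHg, the stated spreads of site size and complete data. The actual number of sites, their sizes and the UK count are not in the documents. The primary conclusion is not in danger if the effects are near those planned. The plan should nevertheless be changed, because its error control relies on each test having its nominal size and the repair is cheap.

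**What to change.** Keep the site-clustered sandwich. In SAP 3.10.2.2, state a bias-corrected version with site-based df for the primary and all subgroup models, for example the Mancl-DeRouen variance (PROC GLIMMIX with EMPIRICAL=FIRORES) on sites − 1 df. Sites − 2 performs about equally well; what matters is naming one before unblinding.

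Carry the df through pooling with EDF= in PROC MIANALYZE. EDF changes the analysis as written by only 0.1-0.3 points. Without it, however, the corrected analysis returns to a near-normal reference and a size of 5.4-6.9%.

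Add the REML compound-symmetry model with Kenward-Roger df as a sensitivity analysis only, given its 2.5-10.4% range under the departures.

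For the run-in-blinding subgroup, report the number of sites per level and treat the heterogeneity p-value as descriptive when one level has few sites. The same reporting is sensible for Region.

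The cost is a short SAP addition, some program changes, one extra model run and the wider interval. Power for 9 mmHg stays at about 99.8%, or 98.8% in the worst case simulated.

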3.10.2.3 Sensitivity Analysis Pooled GMRx2

The primary analysis methods ([Section 3.10.2.2](#)) will be repeated comparing pooled GMRx2 to Placebo. The imputation from the primary analysis and primary analysis methods will otherwise remain unchanged.

3.10.2.4 Adjusted Analyses

Adjusted analyses will be performed as a sensitivity analysis by adding the following covariates: age (continuous), sex, race, BMI category, diabetes and number of treatments at screening. The adjusted treatment effect will be reported as the adjusted least square mean difference and 95% confidence interval.

3.10.2.5 Subgroup and Additional Analyses

Pre-specified subgroup analyses will be carried out irrespective of whether there is a statistically significant treatment effect on the primary endpoint. Subgroups are defined as follows:

- Sex (Male; Female)
- Age (<55; 55-65; > 65 years)
- Race (black; non-black)
- BMI (<30, >=30 kg/m²),
- Diabetic; non-diabetic,
- Region (USA; Other)
- Placebo run-in single-blinded (yes/no)*
- Baseline (at Randomization) home SBP category (<140, 140-149, ≥150 mmHg) and DBP category (<80, 80-89, ≥90 mmHg)
- Number of BP medications at Screening (0, 1)
- Hypertension status at Screening – office BP <140/90 mmHg, ≥140/90 mmHg; office BP <130/80 mmHg, ≥130/80 mmHg
- Orthostatic (postural) hypotension at Randomization (measured at clinic BP): see [Section 3.10.3.2](#) for definitions.

* UK authorities required unblinded run-in period, non-UK centres had single blinded run-in period.

Subgroup analyses will be performed by inclusion of the subgroup main effect as well as two-way interaction terms as fixed effects with treatment within the MM. Heterogeneity of treatment effect between subgroups will be evaluated using contrast statements, to test whether the LS Mean difference between GMRx2 and placebo group differs between levels of the subgroup. Comparisons will be performed separately for each GMRx2 dose level against placebo. A comparison of combined GMRx2 doses against placebo by subgroups will also be performed. LS Means, LS Mean Differences and 95% CIs will be reported for each category of subgroup. If any subgroup does not have sufficient participants for statistical modelling

(i.e., model convergence), descriptive statistics will be provided. A forest plot will also be provided to visualize the overall subgroup analysis.

Sample SAS Code accounting for Sex as Subgroup:

```
PROC MIXED DATA = ADEFF EMPIRICAL METHOD = REML;
  CLASS SITEID SUBJID VISIT TRTP SEX;
  MODEL AVAL = BASE TRTP|SEX / CL;
  REPEATED / SUBJECT = SITEID TYPE = CS;
  WHERE VISIT IN ('WEEK4');
  LSMEANS TRTP*SEX / DIFF CL ALPHA=0.05;
  lsmeans estimate trtp*sex "(TS11-TS31)-(TS12-TS32)"
    [1, 1 1] [-1, 3 1] [-1, 1 2] [1, 3 2]; *TRTP=1 vs TRTP=3;
  lsmeans estimate trtp*sex "(TS21-TS31)-(TS22-TS32)"
    [1, 2 1] [-1, 3 1] [-1, 2 2] [1, 3 2]; *TRTP=2 vs TRTP=3;
  RUN;
```

There is clinical interest in the effects of BP lowering by time of day, particularly through BP in the morning. The telemonitored home BP devices provide a timestamp of each BP measurement taken. Additional analyses will be completed analysing difference between study arms of home SBP by AM and PM time periods.

The clinical use of GMRx2 is expected to involve use in participants who were previously on 0 or 1 medications. As such, a graphical descriptive analysis of blood pressure changes during run-in on placebo will be presented separately for different blood pressure regimens participants were receiving at screening, noting participants could be on 0-1 antihypertensives at the time, before being switched to placebo. Additional descriptive analyses will be conducted according to hypertension control status and number of antihypertensives at screening, including:

- Clinic BP at screening < 140/90 and 0 antihypertensives at screening
- Clinic BP at screening < 140/90 and 1 antihypertensive at screening
- Clinic BP at screening \geq 140/90 and 0 antihypertensives at screening
- Clinic BP at screening \geq 140/90 and 1 antihypertensive at screening

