8.2.1. Inclusion Criteria

At screening visit

1. Provided signed consent to participate in the trial.
2. Adult aged ≥ 18 years.
3. Low calculated CV risk according to local guidelines such that pharmacological BP-lowering treatment is not mandatory: e.g. Pooled Cohorts Equation 10-years ASCVD risk $<10\%$ in the USA.
4. Likely diagnosis of hypertension, defined as one or more of:
 - automated SBP at this clinic visit according to trial methods (see Appendix 2) of ≥ 130 mmHg on no BP lowering medicines or ≥ 120 mmHg on 1 BP lowering medicine that will be stopped at this visit, OR
 - documentation in last 6 months of office SBP ≥ 140 mmHg and/or DBP ≥ 90 mmHg on no BP lowering medicines or SBP ≥ 130 mmHg and/or DBP ≥ 85 mmHg on 1 BP lowering medicine that will be stopped at this visit, OR
 - documentation in last 6 months of home SBP ≥ 130 mmHg and/or DBP ≥ 80 mmHg on no BP lowering medicines or SBP ≥ 120 mmHg and/or DBP ≥ 75 mmHg on 1 BP lowering medicine that will be stopped at this visit, OR
 - documentation in last 6 months of ambulatory daytime SBP ≥ 130 mmHg and/or DBP ≥ 80 mmHg on no BP lowering medicines or SBP ≥ 120 mmHg and/or DBP ≥ 75 mmHg on 1 BP lowering medicine that will be stopped at this visit
5. No contraindication to trial medications, including 2-weeks placebo run-in and 4-weeks randomized treatment period with GMRx2 (dose version 1 or 2) or placebo.

At randomization visit

1. Home seated mean SBP 130-154 mmHg in the week before the randomization visit.
2. Adherence of 80-120% to placebo run-in.
3. Tolerated placebo run-in.
4. Adherence to home BP monitoring schedule: in the week before randomization, at least 6 measures (e.g. ≥ 2 sets of triplicate measures) including at least 1 morning and 1 evening each with ≥ 2 measures. Morning is defined as any measure in the am and evening as any measure in the pm. Morning and evening do not have to be same day.

At week 4 (for optional Open-Label Extension Period)

1. Provided signed informed consent.
2. Completed randomized treatment and willing to continue GMRx2-based treatment regimen for 12 months.

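### Model convergence is not a reliable test for sparse subgroups, and in few-site or small levels the site-clustered sandwich gives confidence intervals that are too narrow and inflated heterogeneity tests

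*SAP*

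**What the plan says.** SAP 3.10.2.2 prescribes in its text a Huber-White variance with compound symmetry by site, and an independence matrix if that model does not converge. SAP 3.10.2.5 carries this into the subgroup models by adding the subgroup and its interaction with treatment. The sample code opens with "PROC MIXED DATA = ADEFF EMPIRICAL METHOD = REML" and clusters on SITEID. No small-sample correction and no degrees-of-freedom method is named.

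For each level the plan reports LS mean differences and 95% CIs. Heterogeneity is tested for each dose against placebo, with a pooled-dose comparison as well, whatever the primary result. SAP 3.10.2.8 puts the results and p-values in a forest plot. SAP 3.3 sets the level: "All tests are to be two-sided with a nominal level of α set at 5"%.

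The only condition for falling back to description is a lack of participants for modelling, which the SAP explains as "i.e., model convergence), descriptive statistics will be provided". No minimum number of participants, placebo participants or sites is given.

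Some listed levels could be small or confined to few sites:
- The top age band, in "Age (<55; 55-65; > 65 years".
- Unblinded run-in, since "UK authorities required unblinded run-in period, non-UK centres had single blinded run-in period".
- Home SBP of 150 mmHg or more, when Protocol 8.2.1 requires "Home seated mean SBP 130-154 mmHg in the week before the randomization visit".
- Diabetes, and orthostatic hypotension at randomization.

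Protocol 8.2.1 also asks for "Low calculated CV risk according to local guidelines such that pharmacological BP-lowering treatment is not mandatory". The Protocol synopsis plans "Approximately 25-30 sites in Australia, Sri Lanka, Nigeria, UK and USA".

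**The concern.** A sandwich estimator takes its variance from the residuals of the clusters that inform the contrast. When these are few, or one arm of a level has only a handful of participants, the fit pulls those residuals towards zero and the standard error shrinks with them. The thinnest rows of the forest plot would then look more precise than they are, and chance differences would appear as heterogeneity. A guard based on convergence would let such rows through. At stake are the subgroup intervals, the forest plot and the heterogeneity p-values, including the comparison of blinded with unblinded run-in, which is a check on trial conduct.

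**Working it through.** **Inputs from the documents.** Two-sided 5% (SAP 3.3); SD 11 mmHg (SAP 2.5); allocation 2:2:1 in permuted blocks within site (SAP 2.3.2); 295 randomized (SAP 2.6.1), so placebo is about 295/5 = 59; 25-30 sites (Protocol synopsis).

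**Assumed, not in the documents.** Site ICC 0.05 (range 0-0.10), 28 unequal sites, baseline slope 0.6, the size and site spread of each level, no missing data, and a t reference with about 260 within-site df.

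**1. The plan's own figures.** For 100 vs 50, SE = 11 × √(1/100 + 1/50) = 1.905, and power for 9 mmHg = Φ(9/1.905 − 1.96) = Φ(2.76) = 99.7%. This matches SAP 2.5, and 13 mmHg gives 100.0%. For 100 vs 100, SE = 11 × √(2/100) = 1.556, and power for 4.5 mmHg = Φ(0.93) = 82.5%, which agrees with Protocol 12.3 (above 80%). Neither document gives a figure for subgroup coverage or interaction error.

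**2. Why the standard error shrinks.** The sandwich is A⁻¹ (Σⱼ sⱼsⱼ′) A⁻¹, with sⱼ = Xⱼ′Vⱼ⁻¹rⱼ for site j. The fit forces Σⱼ sⱼ = 0. If a level exists at one site only, its treatment-by-level columns are non-zero only there, so that site's own score for those columns is exactly zero. Only the shared baseline slope then contributes variance. With two or three sites the scores must still sum to zero, so the shrinkage is smaller but large.

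**3. What convergence detects.** REML iterates on the covariance parameters. In the simulation, boundary or failed fits occurred in 0.5-1.5% of trials at ICC 0.05 and 7-9% at ICC 0, with no relation to level size. An empty treatment cell (45% of trials at 2% prevalence) makes the LS mean non-estimable, which is a different condition from non-convergence.

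**4. Are sparse levels plausible?** If baseline home SBP is normal, truncated to 130-154, the share at 150 or above is [Φ((154−μ)/σ) − Φ((150−μ)/σ)] / [Φ((154−μ)/σ) − Φ((130−μ)/σ)].
- Assumed mean 138, SD 7: (0.989 − 0.957)/(0.989 − 0.127) = 4%, about 2 of 59 placebo participants.
- Assumed mean 142, SD 10: (0.885 − 0.788)/(0.885 − 0.115) = 13%, about 7 of 59.

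**5. Simulation of the SAP model.** 2,000 trials per setting, the same true effect in every level, one dose against placebo, ICC 0.05. The Monte Carlo SE is at most √(0.25/2000) = 1.1 percentage points.

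| Level | Mean n (placebo) | Sandwich SE ÷ true SD | 95% CI coverage | Interaction type I error | Model-based: coverage, error |
|---|---|---|---|---|---|
| 2 sites | 22 (4.3) | 0.38 | 50.6% | 39.1% | 94.4%, 5.5% |
| 3 sites | 32 (6.3) | 0.59 | 69.1% | 24.1% | 95.3%, 5.2% |
| 5 sites | 53 (10.5) | 0.73 | 81.2% | 14.5% | 94.6%, 5.4% |
| 8 sites | 85 (17.0) | 0.83 | 86.6% | 11.3% | 95.6%, 5.6% |
| 14 sites | 148 (29.5) | 0.90 | 90.0% | 7.5% | 95.2%, 4.5% |
| 3% prevalence | 9 (2.2) | 0.49 | 63.0% | 35.2% | 94.8%, 4.9% |
| 5% | 15 (3.1) | 0.63 | 75.3% | 22.7% | 94.4%, 5.5% |
| 10% | 29 (5.9) | 0.83 | 86.6% | 12.1% | 96.2%, 4.0% |
| 20% | 59 (11.8) | 0.91 | 91.1% | 8.1% | 94.5%, 4.9% |
| 50% | 148 (29.6) | 0.94 | 92.4% | 7.6% | 95.1%, 5.0% |

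A rough check is coverage ≈ 2Φ(1.96 × SE ratio) − 1. For 2 sites this is 2Φ(0.745) − 1 = 54%, and for 3% prevalence 2Φ(0.960) − 1 = 66%. Both lie slightly above the simulated values, as expected when the SE itself also varies.

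**6. Robustness.** At 3 sites, ICC 0 or 0.10 gives 23-24% error and 68% coverage. Repeat simulations at ICC 0.05, some with 27 sites and the ICC fixed at its true value, gave 13-38% error and 49-82% coverage for 2-5 sites, and 10-36% and 62-88% for 3-12% prevalence. Keeping the sandwich but using t with (number of subgroup sites − 1) df gives only 89-91% coverage at 2-5 sites and 80% at 5% prevalence, so changing the df alone is not enough.

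**The case against.** The strongest defence has three parts.

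- **The severe figures depend on sizes that the documents do not give.** This stands. The 10% risk limit is an example for the USA only, and no UK or US site count appears. If the UK has eight or more sites, or a level holds 20% of participants, the distortion is modest.
- **Little depends on these analyses.** This also stands. Success rests on the two primary contrasts (SAP 3.3 and 3.10.2.2), Table 3-1 lists the subgroup models as sensitivity analyses, and no claim is tied to an interaction p-value.
- **The code is only an example that may be modified (SAP 2.1).** This helps little, because the text of 3.10.2.2 itself prescribes the sandwich.

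A reader might infer more than the documents support:
- That the convergence guard can never act. REML with compound symmetry is iterative and can fail; the point is that failure does not track sparsity.
- That every subgroup row is unreliable. Large, well-spread levels are close to nominal: a 50/50 split gave 6.5-7.9% error across the simulations.
- That the listed levels are known to be sparse. They are only plausibly so.
- That the primary result is in doubt. The subgroup rule does not enter it.

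**Conclusion.** The point holds, conditional on level size. As written, SAP 3.10.2.5 would present model-based-looking inference for sparse levels with standard errors well below the true sampling variation, and its convergence rule would not reliably stop this. The problem is serious at about five sites or fewer, or about 10% prevalence or less: the test rejects roughly two to eight times as often as the nominal 5%. It is mild for large, balanced levels. The candidates are unblinded UK run-in if UK sites are few, and possibly age above 65, home SBP 150-154 mmHg, diabetes and orthostatic hypotension at randomization. The exact figures rest on the assumed ICC, site sizes and level sizes; the direction follows from the algebra in step 2. It is worth correcting before unblinding, but it is not a threat to the trial's main conclusion.

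**What to change.** In SAP 3.10.2.5, for the subgroup models only:

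1. Drop EMPIRICAL and use model-based standard errors from the same site compound-symmetry model, with Kenward-Roger degrees of freedom. A small-sample-corrected sandwich with suitable degrees of freedom is an alternative.
2. State that convergence is not the criterion for sufficient participants.
3. Optionally, set a minimum number of placebo participants or sites, applied per level so that one sparse level does not make a whole factor descriptive, and fixed before unblinding. The threshold is the sponsor's choice, but its reach should be checked. With 59 placebo participants, a minimum of 10 fails with probability P(Bin(59, p) ≤ 9): 98% at 8% prevalence, 84% at 12%, 61% at 15% and 23% at 20%.

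The cost is a short wording change and a changed option in the model code. There are two downsides. Subgroup standard errors would come from a different estimator than the primary model's. Model-based errors also assume equal variance and no site-by-treatment variation: with a between-site treatment-effect SD of 3 mmHg, type I error was 6.3-7.2% and coverage 93-94% for 2-5 sites, still far closer to nominal than the sandwich.
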